9.0 Data and Safety Monitoring Plan

9.1 Periodic evaluation of data

The study coordinator and the PI will be responsible for the daily oversight of subject safety. Medical history will be reviewed by the study staff, and based on eligibility criteria, any questionable medical histories will be brought to the attention of the medical monitor for final inclusion determination prior to randomization. In a similar manner, contraindications for the treatment products and vital signs will be checked by study staff at each in person visit. The medical monitor will be available via phone for any consultations as necessary.

Participants will be under medical supervision while in the study (i.e., by the medical monitor) and seen on an ongoing basis by our research staff who will document adverse events. The medical monitor will assess all adverse events and will be available for consultation over the phone for urgent matters. Otherwise, the PIs and/or the medical monitor will meet weekly with the study staff to review patient's progress and their experiences with the study products, including any adverse events.

9.2 Data that are reviewed

Data that will be reviewed include:

- Accrual and retention
- Medical history and concomitant medications
- Adverse events and serious adverse events
- Protocol deviations/violations

9.3 Method of collection of safety information

All data, including safety data, will be coded directly into REDCap electronic forms during study visits. Participant adverse events and serious adverse events will be assessed at each in-person study visit and each phone call visit but can be reported at any time during the study.

9.4 Frequency of data collection

Safety data, including adverse events and serious adverse events will be collected at each study contact.

9.5 Individuals reviewing the data

The study coordinator and the PI will be responsible for the daily oversight of subject safety. The PI and/or the medical monitor will meet weekly with the study staff to review participants' progress and their experiences with the study products, including any adverse events. For more urgent and/or serious adverse events, the medical monitor will be available for consultation by phone. The medical monitor will then make any needed medical recommendations and a determination regarding whether the participant is able to continue with the study. Study pulmonologist will review and provide expertise related to CCQ data and all pulmonary AEs.

9.6 Frequency of review of cumulative data

All of the data from the study (including adverse events) will be reviewed by the leadership group, including the PI and the medical monitor, on a regular basis to review patients' progress and their experiences in the study.

9.7 Statistical tests

Statistical methods will be used to analyze the safety data to determine whether harms are occurring. Paired sample t-test (or nonparametric Wilcoxon Rank-Sum test) will be used to examine the changes in the outcome measures (CPD, CO, subjective measures) from the baseline.

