3.0 Inclusion and Exclusion Criteria

3.1 Inclusion Criteria

1. Aged 21-60
2. Smoke filtered cigarettes/machine-rolled cigarettes (≥ 5 cigarettes per day) or daily e-cigarette use for past year
3. No serious quit attempt in prior month. This includes use of any FDA approved smoking cessation medication (varenicline, bupropion [used specifically as a quitting aid], patch, gum, lozenge, inhaler, and nasal spray) in the past 1 month as an indication of treatment seeking.
4. Willing to supplement cigarette smoking with ECIG use for 4 weeks or replace e-cigarette with study product for 4 weeks
5. Willing to attend regular visits over a 4-week period (not planning to move, not planning extended vacation, no planned surgeries)

6. Willing to undergo two fMRI scans
7. Able to read and write in English
8. Able to understand and consent to study procedures
9. Access to computer with internet service that allows for use of Zoom

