7.2.3 Randomization/Pre-Conditioning fMRI Visit (Day 0) – In Person/Remote

Participants will sign their long form written consent at this visit prior to any further study procedures.

Exhaled breath CO (eCO) will be measured at the start of the visit. A urine sample will also be collected and tested for cotinine using the NICCheck cotinine test and pregnancy if participants are of child bearing potential. Eligible participants will then be randomized to one of the four conditions and asked to complete the baseline assessments. This includes the standardized smell test (B-Sit), adverse events assessment and computerized questionnaires of cigarette use, cigarette dependence, liking, and withdrawal as indicated in Table 1. Some of the measures can be done remotely via Zoom, others will need to be completed in person. The remote assessments will be conducted via a Zoom session within 3 days following the scheduled in-Person MRI. The remote visit will only occur after written consent has been obtained. This is being done to limit the amount of face-to-face time during study visits.

Then, participants will complete the fMRI odor cue-reactivity task in the MRI scanner lasting approximately 45 minutes. During the scan, participants will be administered four flavors in separate 4 minutes blocks for eight runs. The flavors will be delivered to the participant's nostrils via tubing from the olfactometer machine. The release of the flavors will be timed with participants' natural rate of respiration and randomized across blocks. At the end of this visit participants will be given the ECIG device and 4-week supply of their randomly assigned flavor cartridges (approximately 2 cartridges/day) and instructed on how to use the device.

Participants will be instructed to take at least 50 puffs per day from the ECIG device to replace conventional cigarette smoking. The participant will be instructed to bring back all used and unused cartomizers to the study center. ECIG puffs per day and cigarettes per day will be recorded on a daily log. Participants will receive a daily REDCap survey link via text message using the Twilio service. Participants will be instructed on how to complete the survey and will be provided with a paper log to tally their cigarette use throughout the day. Participants who are unable or unwilling to receive study text messages will track their cigarette use on the paper log only.

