7.2.5 Post-Conditioning fMRI Visit (Day 28 ± 7 days) – In Person/Remote

Participants will attend a final visit to complete biomeasures, computerized surveys, the adverse events assessment, and the same fMRI tasks as the baseline MRI visit as indicated in Table 1. Some of the measures can be done remotely via Zoom, others will need to be completed in person. The remote assessments will be conducted via a Zoom session ± 3 days of the scheduled in-Person MRI. This is being done to limit the amount of face-to-face time during study visits. eCO will be measured and urine will be collected for cotinine and pregnancy tests. At the end of the visit, participants will be debriefed and counseled on smoking cessation. All participants will be given a copy of the Surgeon General's booklet 'How Tobacco Smoke Causes Disease' (SEE ATTACHMENT: Surgeon General's Booklet).

Table 1: Measures Table (Black X – In Person; Green X – Remote)

	Final Screening	Randomization/ Pre-Conditioning fMRI	Check-In	Post- Randomization fMRI
Visit	1	2	3	4
Day	-7	0	14	28
QUESTIONNAIRES				
Visit Screener	X			
Tobacco Use History	X			
Name Registry	X			
MRI Safety Form	X	X		X
Demographics	X			
Medical History	X			
Concomitant Medications	X	X	X	X
Adverse Event Assessment		X	X	X
Cigarette Details	X			
CCQ (Clinical COPD Questionnaire)	X	X	X	x
Alcohol Audit-C	X			
NIDA Quick Screen	X			
Environmental Smoke Questionnaire	X			
MINI Psychiatric Interview	X			
Daily Smoking and ECIG Use Logs	X (cigarette only)	X	X	X
Cigarette Dependence (Fagerstrom and Penn State Cigarette Dependence Index)		X	X	X
Minnesota Withdrawal Scale		X	X	X
Craving		X	X	X
Cigarette liking scale		X	X	X
ECIG Use History	X	X	X	X
ECIG evaluation scale			X	X
ECIG Side Effects			X	X
ECIG dependence			X	X
ECIG Perceived Health Risk			X	X
ECIP Patterns of Use			X	X
Perceived Benefits and Harms of Using ECIG		X		X
PROCEDURES				
B-SIT Smell Test		X		
fMRI Cue-Reactivity Task in Scanner		X		X
BIOMEASURES				
Pregnancy Test		X		X
Exhaled CO		X		X
Urine Sample Collection		X		X
NICCHECK Rapid Cotinine Test		X		X

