7.2.8 Daily Dairies for ECIG and Cigarette Use

Prior to randomization, participants will be asked to track the number of cigarettes smoked per day using a paper daily diary. They will also receive a daily REDCap survey link via text message (through Twilio) to enter their cigarette usage. During the 4-week ECIG conditioning period, participants will be required to record their ECIG use (in puffs per day) and the number of cigarettes smoked. A paper-based daily diary designed for data collection of each product type will be used. Participants will also continue reporting their use via REDCap survey links each evening. Research assistants will review the data entered by participants via the REDCap survey links at each visit. If participants did not complete the survey online, the researcher will ask the participant at each visit their ECIG and cigarette use. The diary will be used as a memory aid for the participant. (SEE ATTACHMENT: Cigarette Pack Daily Diary and E-cigarette and Cig Daily Diary)

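### Section 9.7 names the Wilcoxon rank-sum test, which is for independent samples, as the fallback for a paired comparison; it should be the signed-rank test

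*Combined protocol and SAP*

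**What the plan says.** Section 9.7 gives the purpose of the analysis: "Statistical methods will be used to analyze the safety data to determine whether harms are occurring". It then names the tests: "Paired sample t-test (or nonparametric Wilcoxon Rank-Sum test) will be used to examine the changes in the outcome measures". The quantities tested are "changes in the outcome measures (CPD, CO, subjective measures) from the baseline". No comparison between arms is mentioned there.

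The schedule confirms that each participant supplies both values:

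- **CO.** At Day 0 (7.2.3), "Exhaled breath CO (eCO) will be measured at the start of the visit". At Day 28 (7.2.5), "eCO will be measured and urine will be collected for cotinine and pregnancy tests".
- **Cigarettes per day (CPD).** Section 7.2.8 starts the log before the intervention: "Prior to randomization, participants will be asked to track the number of cigarettes smoked per day using a paper daily diary". The same section continues it through the four-week conditioning period.
- **Subjective measures.** Table 1 in 7.2.5 schedules, for example, the withdrawal and craving scales at Visits 2, 3 and 4.

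**The concern.** The rank-sum test takes its null distribution from two independent groups. Before and after values from the same people are normally positively correlated, so the difference between them varies less than that distribution assumes. The p-values are then too large, and increasingly so as the correlation rises.

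The error is in the unwelcome direction for an analysis meant to detect harm, because a small or moderate change is more likely to be missed. The fallback may well be needed: CPD is a count, and CO and rating scales may be far from normal. An analyst who follows the text literally runs the wrong procedure. One who silently corrects it departs from the written plan.

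**Working it through.** **Step 1: which test the comparison calls for.** The comparison is within participants. The paired t-test works on within-person differences, and its rank-based counterpart is the Wilcoxon signed-rank test. The rank-sum test is the counterpart of the two-sample t-test.

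**Step 2: whether another reading saves the text.** The rank-sum test would suit a comparison of changes between two arms. But 9.7 offers it in brackets as the substitute for the paired t-test and speaks only of change from baseline. The signed-rank test appears nowhere in the document, and no other section corrects the term.

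**Step 3: inputs.** Section 9.7 states no alpha, sample size or power, so there is no figure to reproduce. The number of participants, 56, comes from 3.3.2, 7.4.3 and 8.1. Everything else is assumed: two-sided 5% level, within-person correlation ρ of 0.1 to 0.7, and the shifts and distributions below.

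**Step 4: type I error by formula.** Under no change, the rank-sum z-statistic has variance of about 1 − ρ_s instead of 1, where ρ_s is the Spearman correlation. For bivariate normal data:

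- ρ_s = (6/π) × arcsin(ρ/2)
- type I error ≈ 2 × [1 − Φ(1.96 / √(1 − ρ_s))]

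At ρ = 0.5, ρ_s = 1.910 × 0.2527 = 0.483. Then √(1 − 0.483) = 0.719 and 1.96/0.719 = 2.72, which gives about 0.6%. At ρ = 0.1, 0.3 and 0.7 the formula gives 3.9%, 2.0% and 0.05%.

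**Step 5: simulation.** 56 normal pairs, 20,000 runs per cell; each cell shows rank-sum / signed-rank rejection rates in %. Shifts are in SDs of a single measurement.

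| Shift | ρ = 0.1 | ρ = 0.3 | ρ = 0.5 | ρ = 0.7 |
|---|---|---|---|---|
| 0 (type I error) | 4.1 / 5.1 | 2.0 / 4.8 | 0.8 / 4.9 | 0.1 / 4.9 |
| 0.3 SD | 33 / 36 | 31 / 44 | 28 / 57 | 24 / 79 |
| 0.6 SD | 88 / 90 | 90 / 95 | 94 / 99 | 97 / 100 |

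At 0.8 SD there is no material difference.

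A second simulation (10,000 runs) fixed the effect at 0.5 SD of the within-person differences. Rank-sum power was 90/80/52% at ρ = 0.3/0.5/0.7, against about 95% for signed-rank. If the test were run within one arm (56/4 = 14 participants), power at ρ = 0.5 was 16% against 39%.

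**Step 6: non-normal data, where a fallback would be used** (56 pairs; first two items at ρ = 0.1/0.3/0.5/0.7).

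- *Lognormal (log-SD 0.8), proportional shift of 0.3 log-SD:* rank-sum 33/31/28/24%, signed-rank 33/40/52/73%.
- *Lognormal, additive shift of 0.3 SD:* rank-sum 81/83/86/91%, signed-rank 64/75/86/97%. Here rank-sum has equal or more power up to ρ = 0.5.
- *CPD with zeros:* eligibility also admits people with "or daily e-cigarette use for past year", some of whom may report no cigarettes at both times. Assume 0, 6 or 14 such participants of 56, with a median of 13 CPD and ρ = 0.5 in the rest. Type I error is then 0.7/0.2/0.0% against about 5%. Power for a 25% fall is 91/72/25% against 98/96/93%.

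**The case against.** The strongest reply is that this is a slip in naming. The term stands directly after the paired t-test, for change from baseline, and an analyst reading the sentence as a whole would very likely run the paired Wilcoxon test. All of the numerical loss depends on someone applying the label literally. That is fair, and it limits the severity. It does not make the written specification correct.

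The figures can also be challenged:

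- **The loss is not uniform.** In the additive lognormal case rank-sum does as well or better up to ρ = 0.5, and for larger shifts on normal data the gap is small. This stands as a limit on the power argument. It does not validate the test, because the null calculation still assumes an independence that these data lack.
- **The inputs to the CPD case are invented.** The plan gives no split between smokers and e-cigarette users and no CPD distribution. If CPD is tested in smokers only, the pattern with no zeros applies.
- **A missed fall in CPD is not a missed harm.** Section 7.4.2 has participants use the e-cigarette in place of cigarettes, and 11.5 lists reduced smoking as a possible benefit. The CPD figures therefore show lost sensitivity only.

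Finally, little depends on the test. No decision rule uses it. Under 9.1, "The medical monitor will assess all adverse events and will be available for consultation over the phone for urgent matters". Suspension under 9.8 follows the medical monitor's review. The primary endpoint (1.2) and the analyses of Aims 1 to 3 (8.3) do not involve it. All of this stands, and it supports a minor rating.

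**Conclusion.** The point holds as a minor error. Section 9.7 specifies a test for independent samples on paired data, and nothing elsewhere in the document corrects it. That conclusion rests on the text alone and needs no assumption.

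The size of the consequence does rest on assumptions. Run as named, the test is slightly conservative at correlation 0.1 and severely so from about 0.5. The material loss of power is confined mainly to small or moderate shifts at such correlations, or to data with many participants at zero both times. The effect is limited to the nonparametric option in the safety analysis.

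**What to change.** In 9.7, replace the name of the Wilcoxon rank-sum test with the Wilcoxon signed-rank test. The rest of the sentence can stand. The cost is one term in one sentence, with no new data, visits or analyses and no effect on any clinical rule.

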1.3 Secondary Study Endpoints

The secondary study endpoints are cigarette dependence, ECIG dependence, ECIG liking and satisfaction, and flavor liking.

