7.4 Test Article(s) (Study Drug(s) and/or Study Device(s))

7.4.1 Description

The ECIG used will be the EGO ECIG. Previous work has shown that the EGO ECIG was capable of delivering nicotine to its users.²⁶ This ECIG is made up of 2 parts, a battery and a cartomizer. The cartomizer contains the heating element and the liquid. The liquid used in the cartomizer will contain either 0 mg/ml or 18 mg/ml of nicotine and be either tobacco or strawberry vanilla

flavor. The nicotine concentration in the liquid and the flavor will be determined by random assignment. The cartomizers will be filled with liquid by the researchers and will be used once by the participant and returned to researchers.

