7.4.2 Treatment Regimen

Participants will be randomized to one of four conditions:

- Tobacco flavor ECIG (18 mg/ml nicotine concentration)
- Tobacco flavor ECIG (0mg/ml nicotine concentration)
- Strawberry Vanilla flavor ECIG (18 mg/ml nicotine concentration)
- Strawberry Vanilla flavor ECIG (0mg/ml nicotine concentration)

Participants will be instructed to use their ECIG for at least 50 puffs per day to replace conventional cigarette use.

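### The Section 9.7 harm test does not separate baseline smokers from non-smoking e-cigarette users, so the group result on cigarettes per day could mask cigarette uptake

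*Combined protocol and SAP*

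**What the plan says.** Section 9.7 (Statistical tests) gives the purpose: "Statistical methods will be used to analyze the safety data to determine whether harms are occurring". The method is a paired t-test, or a nonparametric alternative, which "will be used to examine the changes in the outcome measures (CPD, CO, subjective measures) from the baseline". No subgroup, stratum, arm, significance level or resulting action is named.

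Section 3.1, criterion 2, admits two kinds of participant: "Smoke filtered cigarettes/machine-rolled cigarettes (≥ 5 cigarettes per day) or daily e-cigarette use for past year". The second route sets no cigarette minimum. Criterion 4 gives each kind a different task: "Willing to supplement cigarette smoking with ECIG use for 4 weeks or replace e-cigarette with study product for 4 weeks".

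Section 7.4.2 states the purpose of ECIG use: "Participants will be instructed to use their ECIG for at least 50 puffs per day to replace conventional cigarette use". Section 11.5 counts lower cigarette use as the possible direct benefit. Section 7.4.1 says of the product: "The liquid used in the cartomizer will contain either 0 mg/ml or 18 mg/ml of nicotine". With 1:1:1:1 allocation to four arms (7.4.3), half of all participants are assigned 0 mg/ml. Randomization is stratified by gender and matched for age, not by user type.

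On secondary endpoints, Section 1.3 reads: "The secondary study endpoints are cigarette dependence, ECIG dependence, ECIG liking and satisfaction, and flavor liking". Table 1 schedules cigarette dependence at Visits 2, 3 and 4 without restriction by smoking status.

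**The concern.** The direction that signals harm depends on whether the participant smokes at baseline. In a smoker, fewer cigarettes is the intended effect. In an e-cigarette user with a baseline of zero, any change is an increase and is unwanted. It is also foreseeable, because these participants give up their own product and half of all participants are assigned liquid without nicotine.

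If one mean change is tested over everyone, a fall in smokers can outweigh uptake in non-smokers. The only statistical test that the plan offers for harm could then report a significant improvement while some participants start or return to smoking. There is also a smaller effect in the other direction: non-smokers who stay at zero dilute the change seen in smokers.

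**Working it through.** **Inputs from the documents.** 56 randomized (Section 8.1); two entry routes (3.1); four equal arms, two at 0 mg/ml (7.4.2, 7.4.3). Section 9.7 gives no figure to reproduce. The documents give no share of e-cigarette users, no CPD mean or SD and no uptake rate, so every size below rests on stated assumptions.

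**Algebra.** Let f be the share of participants with zero baseline CPD, X the mean fall in smokers, and Y the mean rise over all zero-baseline participants, including those who do not take up smoking.

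Overall mean change = -(1 - f)X + fY.

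With X = 5 and Y = 3 (assumed):

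- f = 10%: -4.5 + 0.3 = -4.2
- f = 25%: -3.75 + 0.75 = -3.0
- f = 50%: -2.5 + 1.5 = -1.0

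The mean is zero at f = X/(X + Y) = 5/8 = 62.5%. In general it turns positive only if Y > X(1 - f)/f:

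- f = 25%: Y must exceed 3X, which is 15 CPD for a fall of 5
- f = 50%: Y must exceed X
- f = 75%: Y need only exceed X/3

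**Dilution.** With Y = 0 and f = 25%, a 5 CPD fall in smokers appears as 0.75 × 5 = 3.75, a 25% reduction.

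**Simulation of the test.** N = 56, two-sided 0.05, 20,000 runs per case. Smokers' change is normal with mean -5 and SD 5 (assumed). Among zero-baseline participants, either 30% take up about 3 CPD (mean rise 0.9) or 50% take up about 5 CPD (mean rise 2.5).

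| Zero-baseline participants | Uptake | Overall mean change | Overall test: significant fall | Overall test: significant rise | Separate t-test in zero-baseline group: significant rise |
|---|---|---|---|---|---|
| 7 of 56 | 30% × 3 | -4.26 | 100% | 0% | 11% |
| 7 of 56 | 50% × 5 | -4.06 | 100% | 0% | 50% |
| 14 of 56 | 30% × 3 | -3.52 | 100% | 0% | 55% |
| 14 of 56 | 50% × 5 | -3.14 | 99.7% | 0% | 97% |
| 28 of 56 | 30% × 3 | -2.05 | 96% | 0% | 96% |
| 28 of 56 | 50% × 5 | -1.25 | 33% | 0% | 100% |
| 42 of 56 | 30% × 3 | -0.58 | 8% | 0% | 99.9% |
| 42 of 56 | 50% × 5 | +0.62 | 0% | 11% | 100% |

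With 28 of 56 and falls of 3 to 8 CPD, the overall test shows a rise in at most 0.4% of runs. Masking weakens when non-smokers dominate: with 42 of 56, a fall of 3 and 50% uptake of about 5 CPD, the overall test shows a rise in 52% of runs. With only 7 non-smokers, a separate t-test also has little power, so splitting the test alone is not enough.

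**The case against.** **A reader might infer that the plan would hide uptake. It would not.** Cigarettes are logged daily, staff review the entries at each visit (7.2.8), use is discussed at the Day 14 visit (7.2.4), and the leadership group reviews all study data regularly (9.6). With 56 participants, a vaper who starts smoking should be visible individually. What remains is narrower. The adverse event question asks about symptoms (7.2.6), the list of reviewed data in 9.2 omits CPD and CO, and no signal or summary of uptake is defined.

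**Pooling is read from silence.** Section 9.7 neither requires nor excludes a split, and Aim 1 in 8.3 does distinguish user types. That is fair, but followed as written 9.7 is a single test per measure.

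**The non-smoking group may be small.** Criterion 2 does not require e-cigarette users to be non-smokers, and Section 7.4.4 describes participants as continuing to smoke. The share with zero baseline is therefore unknown. A small share means fewer people at risk, but it is also where masking of the mean is strongest.

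**A reader might extend the netting to CO.** The documents do not support this. Both CO readings follow an instructed 14-hour abstinence (7.2.2, 7.2.4), which should blunt a fall in smokers and a rise from uptake alike.

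**A reader might say cigarette dependence means nothing in non-smokers.** That goes too far, because dependence emerging from zero would be informative if uptake occurred. What stands is that non-smokers dilute the change in those who smoked at baseline.

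**No decision is tied to the 9.7 test.** Suspension rests on the medical monitor's review and the IRB (9.8, 18.11), and the primary endpoint is fMRI. This limits the consequence to how harm is reported.

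**Conclusion.** The point holds for the group-level test of CPD. Section 9.7 does not separate participants for whom a fall is expected from those who can only stay at zero or rise. The result could therefore show no increase, or a significant decrease, while non-smokers take up cigarettes, unless non-smokers are a clear majority. Under the assumed changes of -5 and +3 CPD, that means more than 62.5% of the sample. The direction of the problem follows from the eligibility criteria and the ECIG instructions. Its size rests entirely on assumed values for the share of non-smokers, the fall and the uptake.

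It does not show that uptake would go unseen, that CO nets out in the same way, or that the primary analysis is affected. It is an inexpensive improvement to a stated safety analysis and worth making.

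**What to change.** Amend Section 9.7 as follows:

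- Report change in CPD and CO separately for participants with and without any cigarette use in the pre-randomization daily log. Splitting by logged use, not by entry route, places e-cigarette users who also smoke correctly.
- For participants without such use, report by nicotine arm the number and proportion with any cigarette use after randomization, from the daily log. Show their CO alongside as a supporting objective check, and note that the 14-hour abstinence limits it.
- Report change in cigarette dependence in baseline smokers.

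The cost is a few sentences. The logs, CO and dependence scales are already collected. The downside is smaller groups. For example, 14 non-smokers would give about 7 per nicotine level on average, and user type is not a randomization stratum. The non-smoker result should therefore be a count or listing, not a significance test.
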